I have read the protocol, including all appendices, and I agree that it contains all of the necessary information for me and my staff to conduct this study as described. I will conduct this study as outlined herein, in accordance with the regulations stated in the International Conference on Harmonisation guidelines, and will make a reasonable effort to complete the study within the time designated.

I will provide all study personnel under my supervision copies of the protocol and any amendments, and access to all information provided by ONL Therapeutics or specified designees. I will discuss the material with them to ensure that they are fully informed about ONL1204 Ophthalmic Solution and the study.

Principal Investigator Name (printed)

Signature

Date

Site Number

Page 4 of 52

Study Summary

Title:	A Phase 1 Open-Label, Dose Escalation Study to Assess the Safety and Tolerability of Intravitreal ONL1204 in Patients with Macula-off, Rhegmatogenous Retinal Detachment.
Rationale:	The purpose of this study is to evaluate the safety and tolerability of ONL1204 in Patients with Macula-off, Rhegmatogenous Retinal Detachment (RRD). RRD is an acute and serious vision threatening condition in which a tear in the retina, typically resulting from a vitreous detachment, allows liquefied vitreous to enter the subretinal space, detaching the photoreceptor (PR) layer of the neurosensory retina from the retinal pigment epithelium (RPE). As the RPE is the principal source of nutritional support for the PR layer, the photoreceptor cell death is the primary mechanism of vision loss after retinal detachment.
	ONL1204 is a first-in-class inhibitor of Fragment Apoptosis Stimulator receptor (Fas)-mediated cell death. ONL1204 has demonstrated protection of multiple retinal cell types in numerous preclinical models of acute ocular injury.
	This will be a first-in-human (FIH) study to evaluate safety and tolerability of a single-dose of ONL1204 in patients with macula-off RRD.
	The standard of care for surgical repair of macula-off RRD is reattachment surgery (typically by vitrectomy with or without scleral buckling) within 7 days of the macula detaching. Patients will receive a single intravitreal injection upon enrollment in the study on the day of diagnosis. The vitrectomy procedure will remove the bulk of drug remaining in the vitreous.
Target Population:	Patients who present between 1 week (7 days) to 4 weeks (28 days) of a macula-off RRD (based on patient-reported history of loss of central vision) for whom standard retinal reattachment surgery by means of a pars plana vitrectomy and gas tamponade is indicated.

Number of	Approximately 16 patients will be enrolled in this study.								
Patients:	• 4 ascending dose groups; 4 active. The first patient in each dose group will be observed for at least 14 days post-surgery (through visit 6) prior to enrolling the remainder of the patients in that dose group.								
	• Patients may be replaced who do not receive an injection of study medication, or for discontinuing from the study for reasons unrelated to treatment before completing Visit 4. All patients receiving injection of study drug will be followed for safety and tolerability.								
Study Visits	There is a minimum of 8 scheduled study visits:								
	• Visit 1: Day 1 (baseline/drug injection)								
	• Visit 2: Day 2 (1 day post-injection*)								
	• Visit 3: Day of Vitrectomy (3 + days post-injection in accordance with standard of care vitrectomy)								
	• Visit 4: Postoperative visit (1 day post-surgery)								
	• Visit 5: Post-operative visit (2 weeks post-surgery and clearance of sentinel patient/cohort (14 days +4 days post-surgery))								
	• Visit 6: Week 6 (±7 days)								
	• Visit 7: Week 9 (±7 days)								
	• Visit 8: Week 24/Exit (±14 days)								
	*additional visits between visit 2 and 3 per investigator's discretion								
Objectives:	To evaluate safety and tolerability of a single intravitreal injection of ONL1204 in patients with macula-off, RRD.								
Study Design:	This is a single-injection, open-label dose escalation study.								
Primary Objective:	The primary objective will be to determine the Maximum Tolerated Dose (MTD) of ONL1204 and select doses for Phase 2. Determination of this will be through review of the parameters measured in the Schedule of Assessments, as well as adverse event (AE) reports.								

Page 6 of 52

Exploratory Objective: During the study, ocular fluid samples will be collected at the time of study drug injection and at the time of vitrectomy. These samples will be used for pharmacokinetic and pharmacodynamic analyses, the results of which will help inform the dose selection for the Phase 2 trial(s).

Page 7 of 52

STUDY SCHEMATIC

Figure 1 Study Schematic

16 patients will be enrolled and treated, starting with the lowest dose, Cohort 1. The first patient in each cohort will be observed for at least 14 days post surgery (through Visit 5) before the rest of the cohort can be enrolled. The safety review committee will review the data prior to clearing the sentinel patient and enrolling the remainder of the cohort. After all 4 patients in a cohort have completed Visit 5, the safety review committee will review available safety data to determine if dose limiting toxicity exists that prohibits enrolling the next higher dose cohort. The respective IRB's will be informed of the outcome of the SRC meetings.

If there are no safety concerns, the next cohort will start treatment.

*Patients may be replaced who do not receive an injection of study medication, or for discontinuing from the study for reasons unrelated to treatment before completing Visit 4.

Page 8 of 52

TABLE OF CONTENTS

CLINICAL RESEARCH PROTOCOL						
Clinical Protocol Approval Form2						
Confidentiality and Investigator Statement						
Study Summary	4					
TABLE OF CONTENTS	8					
Table of Tables	.10					
Table of Figures	.10					
LIST OF ABBREVIATIONS	.11					
1 INTRODUCTION AND RATIONALE	.14					
1.1 Background	.14					
1.2 ONL1204	.14					
1.2.1 Preclinical Experience	.14					
1.2.2 Clinical Experience	.16					
1.3 Study Rationale	.16					
1.3.1 Rationale for the Proposed Doses	.16					
1.3.2 Rationale for Pharmacokinetic testing	.17					
1.3.3 Rationale for Vitreous Tap and Pharmacodynamic Analysis	.17					
1.4 Potential Risks and Benefits	.18					
1.4.1 Potential Risks of Study Product	.18					
1.4.2 Potential Risk to Fetal Development	.18					

1 INTRODUCTION AND RATIONALE

1.1 Background

Retinal detachment is an ocular condition that involves the retina being separated from the underlying layer of cells, including the retinal pigment epithelium (RPE). This separation often results in the death of key retinal cells, including photoreceptors, which can lead to vision impairment and/or loss.

The most prevalent form of retinal detachment is rhegmatogenous retinal detachment (RRD), which involves a tear in the retina. While standard of care (SOC) surgical reattachment results in high rates of anatomic surgical success, in many cases, especially those involving the macula (central vision), patients have significant loss of vision even with successful surgery. In part, this is due to the fact that photoreceptors begin to die once the detachment takes place and cell death continues up to the time of surgery (sometimes as long as a week after the detachment).

ONL Therapeutics (ONL) is developing ONL1204, a first-in-class inhibitor of Fragment Apoptosis Stimulator (Fas)-mediated cell death that has demonstrated protection of multiple retinal cell types in numerous preclinical models of acute ocular injury. The development of ONL1204 addresses an unmet medical need: the prevention of vision loss in patients suffering from deterioration of visual function after acute retinal injury such as from macula-off RRD.

Refer to the Investigator's Brochure (IB) for more information.

1.2 ONL1204

The investigational study agent is ONL1204 Ophthalmic Solution. The drug product consists of the drug substance ONL1204 dissolved in a vehicle consisting of purified water containing mannitol, poloxamer 407, and glacial acetic acid. The pH is adjusted to pH 4.5 by sodium hydroxide solution. ONL1204 Ophthalmic Solution is provided as a sterile liquid in single-use vials stored at 2 to 8°C (36 to 46°F) and is administered by intravitreal (IVT) injection.

1.2.1 Preclinical Experience

The sponsor has observed a pharmacological effect of ONL1204 in preventing Fasmediated cell death in 3 models of acute retinal injury – namely the rat retinal detachment model, the rabbit sodium iodate model, and the mouse microbead model of glaucoma.

ONL1204 disrupts the binding of human Fas ligand to the human Fas receptor in vitro, while ONL1204 analog Met12 has been shown to bind to Fas receptor and prevent Fas

ligand activated cell death in human Jurkat cells in vitro. The available nonclinical data from completed studies indicates that ONL1204 has efficacy towards the Fas ocular receptor based on the in vitro inhibition of caspase activity with a potency of 0.4 to 0.45μ M.

In vivo, administration of ONL1204 by IVT injection at doses of up to 10 μ g/eye resulted in a reduction of terminal deoxynucleotidyl transferase (dUTP) nick end labeling (TUNEL) positive staining cells in a rat model of retinal detachment. There was an approximate 75% reduction in the percent positive staining cells across the dose range examined. The minimal, maximally effective dose for ONL1204 was 0.1 to 0.3 μ g. Pharmacological activity towards the Fas receptor did not differ with different formulations of ONL1204, though poloxamer formulations appeared to have preferable pharmaceutical properties.

To study the potential role of ONL1204 in geographic atrophy, ONL conducted a sodium iodate study in rabbits. Sodium iodate is highly toxic to the retinal pigment epithelium and is a commonly used model for geographic atrophy. IVT injection of ONL1204 at 0.1 or 0.025 mg 4 days prior to sodium iodate injection preserved the RPE, suggesting that ONL1204 may also be useful in treating geographic atrophy.

In a microbead model of glaucoma, data suggest that ONL1204 can also inhibit the production of macrophage and Receptor Interacting Protein Kinase 3 (RIPK3)-dependent inflammasome activation, which exacerbates retinal detachment-induced photoreceptor cell death through the release of interleukin (IL)- 1β .

In pharmacokinetic (PK) studies, ONL1204 is distributed to the retina, iris-ciliary body (ICB), and vitreous with IVT injection. Following injection, the drug is slowly eliminated from these ocular structures. The prolonged elimination of the drug is considered clinically meaningful for use in RRD where patients may not undergo surgical repair for several days following injection. However, the clinical plan for retinal detachment includes a vitrectomy within 7 days after injection, which will remove the bulk of the drug remaining in the vitreous.

Based on the pharmacodynamic (PD) and preliminary toxicity data, ONL has chosen the 4.5% mannitol, 0.4% poloxamer 407, and 10 mM acetic acid (pH 4.5) formulation to be used in further development of ONL1204. There was acceptable (minimal to mild) ocular toxicity in the rabbit with this formulation and the current drug formulation of ONL1204. Moreover, ONL1204 was undetectable in the rabbit plasma (lower limit of quantification [LLOQ]: 1 ng/mL) following a total dose equal to the planned top dose in humans resulting in no systemic toxicity after full histopathologic examination of all major organs.

Good Laboratory Practice (GLP) compliant toxicity studies using this formulation of ONL1204 are completed.

Preclinical data thus far indicate the intended clinical formulation at the top dose $(200 \ \mu g)$ to be used in clinical trials should have an acceptable safety profile over a 14-day period following IVT injection.

Refer to the IB for detailed information on the nonclinical studies conducted using ONL1204.

1.2.2 Clinical Experience

ONL1204 has not been previously studied in humans; this will be the first-in-human (FIH) study of ONL1204. Since there are no clinical data for ONL1204, the observed findings in nonclinical studies with ONL1204 will guide the monitoring in this study.

1.3 Study Rationale

The purpose of this Phase 1 study is to collect safety information of ONL1204 in patients, establish a safe dose range, and collect PK and ocular PD information.

The study population will be patients with newly diagnosed macula-off RRD. Patients with RRD have an acute and serious vision threatening condition where a tear in the retina, typically resulting from a vitreous detachment, allows liquefied vitreous to enter the subretinal space, thereby detaching the photoreceptor (PR) layer of the neurosensory retina from the RPE. As the RPE is the principal source of nutritional support for the PR layer, the photoreceptors begin a cascade of inflammation and cell death. Nonclinical data on ONL1204 suggest that ONL1204 may inhibit the cell death pathway in RRD, preventing vision loss in patients suffering from acute retinal injury such as from macula-off RRD.

In clinical use, ONL1204 will be delivered to patients by intravitreal injection at the time of diagnosis to protect photoreceptors from death until surgery can be completed, with the hope of improving positive patient outcomes from already anatomically successful surgeries.

1.3.1 Rationale for the Proposed Doses

As described in 1.2.1 the minimal, maximally effective dose in the rat model of retinal detachment delivered by an IVT injection was 0.1 to 0.3 ug per eye. Based on scaling of this MMED from the rat eye to the human eye, the calculation is as follows: the vitreous volume of a rat eye is 13-20 microliters, while that of the human is approximately 4,400 microliters (a factor of 220-338x). With the MMED being estimated at 0.1 micrograms in the rat, this scales to a dose of 22-34 micrograms in the human eye. This dose escalation study starts at a 25 microgram dose and increases to 50 micrograms in the next

cohort, followed by a 100 microgram cohort and 200 micrograms in last dose escalation cohort.

As stated, the maximum dose planned for this trial is $200 \ \mu g$. In animal studies, using Dutch Belted rabbits, this dose was intravitreally injected into one eye while the contralateral eye served as an untreated control. The findings from this study suggested the current formulation at the top dose ($200 \ \mu g$) to be used in GLP-compliant nonclinical studies and in clinical trials should have an acceptable safety profile over a 14-day period following IVT injection, especially given that the allometrically scaled dose in the rabbit is approximately 2-fold greater than the planned high dose intended for this initial clinical trial.

The following doses will be evaluated: $25 \ \mu g$, $50 \ \mu g$, $100 \ \mu g$ and $200 \ \mu g$ ONL1204. ONL1204 will be administered as a sterile liquid by intravitreal injection. Patients randomized to receive the treatment will be given one injection of the drug.

1.3.2 Rationale for Pharmacokinetic testing

Systemic PK will be evaluated following IVT administration of ONL1204. ONL1204 is not expected to be detected in the plasma and this will be confirmed in this study, which will preclude additional systemic PK evaluation in future studies.

ONL1204 will also be measured in the vitreous samples taken at the time of the vitrectomy to evaluate clearance of the drug from the vitreous.

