4.2.2 Dose Escalation Decisions

Dose escalation decisions include the following:

- 1. To begin enrolling the next cohort at the planned dose or an adjusted dose.
- 2. To delay opening the next cohort in order to collect additional safety on the current cohort, or to enrol additional patients in the current cohort if safety concerns are identified.
- 3. To stop the cohort escalation if unacceptable toxicities are noted.

If, in the opinion of SRC, dose limiting toxicity is reached, the previous, lower dose will be considered the Maximum Tolerated Dose (MTD).

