Study Visit	Visit 1 Day 1 Baseline ² / Injection			Visit 2 Day 2 (¹ ,	Visit 3 (Day 4 +)	Visit 4	Visit 5	Visits 6, 7	Visit 8	Unscheduled Visit(s)
				1 day Post- Injection	3 + days Post- Injection) Day of Surgery (Vitrectomy) ³	1 Day Post- Surgery	14 Days (±4 days) Post- Surgery	Weeks 6, 9 (±7 days)	Week 24 (±14 days) Exit or early termination	
Assessment	Pre- Injection	Study Drug IVT	Post- Injection							
Blood Sampling for Plasma ONL1204 PK			X ⁵	X	X		X	X ⁶	X	
Study Drug IVT		X								
Pin Hole Visual Acuity						OU				
Low Luminance ETDRS Best Corrected Visual Acuity								OU	OU	
Low Contrast ETDRS Best Corrected Visual Acuity								OU	OU	
Contrast Sensitivity Testing								OU	OU	
Farnsworth D15 Color vision test									OU	

⁵ Post-injection blood sample for plasma PK to be drawn 1 hour (\pm 15 minutes) after study drug IVT. ⁶ Blood sample for plasma PK to be drawn only on Visit 7 (week 9)

Page 27 of 52

Study Visit Visit 1 Visit 2 Visit 3 Visit 4 Visit 5 Visits 6, 7 Unscheduled Visit 8 Day 2 (¹, Day 1 (Day 4 +) Visit(s) Baseline²/ Injection 3 + days Post-1 day 1 Day Post-Week 24 14 Days Weeks 6, 9 (±7 Injection) (±14 days) Post-Surgery (±4 days) days) Injection Day of Post-Exit or early Surgery Surgery termination (Vitrectomy)³ Pre-Study Post-Assessment Injection Drug Injection IVT Intraocular SE⁴ OU OU SE OU OU OU OU Pressure⁷ Slit Lamp SE⁴ OU OU OU SE OU OU Biomicroscopy Indirect SE⁴ OU OU OU SE OU OU Ophthalmoscopy Fundus OU OU Photography **ONL1204** Fundus OU Autofluorescence B Scan SE Ultrasonography (optional) SD OCT OU OU SE SE

Note: Screening procedures are in red

Abbreviations: AE = Adverse event; ETDRS = Early Treatment Diabetic Retinopathy Study; IOP = Intraocular pressure; PK = Pharmacokinetic;

Post-op = Postoperative; OU = Both eyes; SD OCT = Spectral Domain Optical Coherence Tomography; SE = Study eye; UA = Urine analysis.

⁷ iCare Tonometry and Tonopen methods of measurement are acceptable.

Page 28 of 52

Study Visit	Visit 1 Day 1			Visit 2 Day 2 (¹ ,	Visit 3 (Day 4 +)	Visit 4	Visit 5	Visits 6, 7	Visit 8	Unscheduled Visit(s)
	Baseline ² / Injection			1 day Post- Injection	3 + days Post- Injection) Day of Surgery (Vitrectomy) ³	1 Day Post- Surgery	14 Days (±4 days) Post- Surgery	Weeks 6, 9 (±7 days)	Week 24 (±14 days) Exit or early termination	
Assessment	Pre- Injection	Study Drug IVT	Post- Injection							
Vitreous Tap for Cytokine / Biomarker Analysis	SE									

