- Actual Time from First Dose (hours) = (Date/Time of First Dose PK Sample collection) (Date/Time of First Dose)
- Actual Time Deviation (hours) = (Actual PK Sample Collection Time Post Dose) (Scheduled PK Sample Collection Time Post Dose).
- Treatment Emergent Adverse Events (TEAEs) are defined as adverse events that occurred following the first administration of study medication.

Inferential Analyses

Descriptive statistics will be used to summarize the safety, PD and PK data. No formal hypothesis testing is planned.

Multiple Comparisons and Multiplicity Adjustments.

Not applicable for this study.

Handling of Missing Data

For the classification of Treatment emergent adverse event (TEAE) and Concomitant medication, the following will be applied in the following order:

- a. If all dates/times (start and stop) missing, the event/medication will automatically be classified as a TEAE/Concomitant medication.
- b. For AEs with a missing start date/time, if the event end date/time is prior to first study drug administration, the event will not be classified as a TEAE.
- c. If only the AE start year/ medication end year is present and is the same or is after the first study drug administration year unit, the event/medication will be classified as a TEAE/Concomitant medication.
- d. If the AE start month and year/medication end month and year are present and are the same or after the first study drug administration month and year units, the event/medication will classified as a TEAE/Concomitant medication.

For plasma concentration-time data/profiles and PK analysis the following will be applied:

- a. Concentrations that are below limit of quantification (BLQ) prior to the dosing (Pre-dose) will be set equal to zero. Post dose BLQ concentrations will be set to zero.
- b. Where there are no results, these will be set to missing.
- c. If more than 75% of values per nominal timepoint and treatment group are BLQ, then all descriptive statistics, except for nBLQ, will be denoted as not calculable (NC).
- d. For the purpose of calculating the non-compartmental plasma PK parameters, concentrations that are BLQ prior to the first quantifiable value will be set equal to zero and BLQ values after measurable concentrations will be set to zero.
- e. For the calculation of summary statistics of plasma PK parameters, all NR (not reported) and NC (not calculable) values in a data series will be set to missing.

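### Protocol 1.3.2 promises to confirm that no drug reaches plasma and to rule out later systemic PK, but it sets no criterion, and four patients per dose cannot support that conclusion

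*Protocol*

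**What the plan says.** Protocol 1.3.2 states the expectation that the drug will not be found in plasma, and continues: "this will be confirmed in this study, which will preclude additional systemic PK evaluation in future studies".

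The evidence available to support this is as follows.

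- **Patients.** The Study Summary says "Approximately 16 patients will be enrolled in this study", and the study schematic text has four per dose: "After all 4 patients in a cohort have completed Visit 5". The doses are 25, 50, 100 and 200 µg. Protocol 4.2.2 lets the committee change the dose, stop escalation, or decide "to enrol additional patients in the current cohort if safety concerns are identified".
- **Statistics.** Protocol 9.1.1 and 9.1.2 have no hypothesis and no sample size calculation. SAP Section 3 is descriptive.
- **Assay.** The only LLOQ given is from the animal work (Protocol 1.2.1): "ONL1204 was undetectable in the rabbit plasma (lower limit of quantification [LLOQ]: 1 ng/mL", at a total dose equal to the human top dose.
- **Sampling.** Table 4-1 marks plasma samples after injection, on Day 2, on the day of surgery before vitrectomy, 14 days after surgery, at Week 9 and at Week 24. Footnote 5 fixes the first: "Post-injection blood sample for plasma PK to be drawn 1 hour" after injection, with a 15-minute margin.
- **Reporting.** Protocol 9.3.1.7 and SAP Section 3 give counts of values below the LLOQ (BLQ) at each time point. SAP 10.1 bases the plasma summary tables on the plasma PK population.

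**The concern.** The protocol writes down both the result and its consequence for the whole programme before any human has been dosed. Nothing says what would count as confirmation: no number of patients, no tolerable detection rate, no concentration, no human LLOQ. A team following the text could read four clean patients at the top dose as licence to leave systemic PK out of every later study. Protocol 1.4.1 lists a systemic adverse reaction as a potential risk, so the measurement that would be dropped is a safety-related one.

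The phrase about future studies is also unlimited in scope. This trial gives a single injection followed by vitrectomy, which Protocol 1.2.1 expects to remove most of the drug remaining in the vitreous. The same section mentions geographic atrophy as a possible use, and the documents describe no vitrectomy in that setting. A clean result here would not carry over automatically.

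**Working it through.** **1. The plan's own figures.** 4 cohorts × 4 patients = 16, which agrees with the stated total. There is no power, alpha or precision figure to reproduce.

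**2. What zero detections would show.** With 0 of *n* patients detected, the exact (Clopper-Pearson) upper limit solves (1 − p)^n = α. So p = 1 − 0.05^(1/n) one-sided, and p = 1 − 0.025^(1/n) two-sided.

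| Patients with no detection | One-sided 95% limit | Two-sided 95% limit |
|---|---|---|
| 0/4 (200 µg) | 52.7% | 60.2% |
| 0/8 (100 and 200 µg) | 31.2% | 36.9% |
| 0/16 (all doses) | 17.1% | 20.6% |

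The pooled rows describe a mix of doses. Twelve of the 16 patients receive between 1/8 and 1/2 of the top dose.

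**3. How easily a clean cohort arises.** P(0/4) = (1 − p)^4. For true detection rates of 10%, 20%, 30% and 50% this is 65.6%, 41.0%, 24.0% and 6.3%.

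**4. Patients needed.** n = ln(0.05)/ln(1 − p), rounded up. To put the one-sided limit below 50%, 25%, 20%, 10% or 5% takes 5, 11, 14, 29 or 59 patients at one dose, all without detection.

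**5. The assay floor.** Assume a plasma volume of 2.5 to 3.5 L (not in the documents) and a human LLOQ of 1 ng/mL, as in the rabbit. A level just under the floor then corresponds to 2.5 to 3.5 µg in plasma at one time. That is 1.25% to 1.75% of 200 µg, or 10% to 14% of 25 µg.

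**6. Which cohorts are informative.** Assume 3 L, a vitreous half-life of 2 to 10 days (48 to 240 h) and a plasma half-life of 0.25 to 2 h; none of these is in the documents. The approximate steady level is dose × t(plasma) / (t(vitreous) × 3 L).

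| Dose | Low: 0.25 h, 240 h | High: 2 h, 48 h |
|---|---|---|
| 25 µg | 0.009 ng/mL | 0.347 ng/mL |
| 100 µg | 0.035 ng/mL | 1.389 ng/mL |
| 200 µg | 0.069 ng/mL | 2.778 ng/mL |

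Both upper doses straddle 1 ng/mL. At the low corner neither would be detected.

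**7. The reporting denominator.** SAP 4.1.4.2 requires a profile evaluable for at least one of Cmax, Tmax or AUC, and SAP 10.1.1.4 requires three consecutive values above the LLOQ for an AUC. A patient whose values are all BLQ may therefore fall outside the population used for the summary tables, although such patients are the evidence for non-detection. The planned BLQ counts are per time point. They do not give the number of patients with any detectable value.

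**The case against.** The strongest reply is that this is one rationale sentence. It opens with an expectation, plasma PK is an exploratory endpoint, and the SAP plans a non-compartmental analysis wherever the data allow. No endpoint or decision within this trial depends on the sentence. That stands, and it keeps the severity low.

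The binomial limit also ignores the rabbit evidence: plasma was undetectable at a total dose equal to the human top dose, and Protocol 1.3.1 puts the scaled rabbit dose at about twice the human one. That supports an expectation of low exposure. It does not confirm it in humans.

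BLQ counts by time point and a concentration listing are already planned. The per-patient count, its denominator and the exact limit are not.

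Three stronger readings are tempting, and the documents do not support them.

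- *Only the top dose can test the claim, because lower doses must fall below the floor.* Step 6 shows that 100 µg can exceed 1 ng/mL under the same assumptions, and the human LLOQ is unknown.
- *The gap between 1 hour and Day 2 would miss the peak.* With one plasma compartment and first-order release from the vitreous, over the corner cases of step 6, the peak falls at 1.9 to 13.9 h. The better of the 1 h and 24 h samples catches 85% to 98% of it. The gap matters little unless release is not slow.
- *No pre-dose sample is taken, so non-detection cannot be shown.* Table 4-1 marks none, but footnote 2 can be read as allowing a draw with the baseline laboratory tests. The SAP sampling list in 10.1 opens with an empty bullet, and a SAP rule presumes such a sample: "Concentrations that are below limit of quantification (BLQ) prior to the dosing (Pre-dose) will be set equal to zero". The documents are unclear on this. In a first-in-human study of a drug not previously given to anyone, a pre-dose value would help only to interpret a positive reading.

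**Conclusion.** The point holds as a minor one. Protocol 1.3.2 promises a confirmation that the design cannot deliver and attaches to it a consequence for all later studies. With no detections at 200 µg, a true detection rate of about one half is not excluded. Even all 16 patients leave about one in six (one-sided) or one in five (two-sided).

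These limits need only independent patients and full cohorts of four; a cohort that is enlarged or never opened would change them. They do not rest on the pharmacokinetic assumptions in steps 5 and 6, which serve only to show what the floor might hide and which doses are informative. The most the study can report is the number of patients below the LLOQ at the sampled times, by dose, in this surgical setting. The evidence for negligible exposure would be limited but not absent, and nothing here suggests that exposure is in fact high.

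**What to change.** 1. **Protocol 1.3.2.** Say that plasma exposure will be assessed. Delete the clause on future studies, or limit it to the doses and setting studied. State the human LLOQ.
2. **SAP Table 14.2.1.** Add one line giving, by dose, the number of patients with any post-dose plasma value at or above the LLOQ, with the LLOQ and the exact upper 95% limit. The denominator should be all dosed patients with a plasma sample, not the plasma PK population.
3. **Pre-injection sample.** Reconcile Table 4-1, its footnote 2 and the SAP pre-dose rule on whether a plasma sample is taken before injection.

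The new table line needs no new data. The cost is a less favourable stated conclusion, one SAP line and a small wording amendment, which under Protocol Section 12 goes to the ethics committee.
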